### **Study Procedures for Informed Written E-Consent via HIPAA compliant Zoom Videoconferencing and REDCap**

Participants will be sent an email or text to their study funded smartphone with the REDCap link to the IRB-approved ICF. This link will be sent by a member of the NYU ACCESS II RCT research team. Once the link is received, a date and time will be scheduled for an IRB approved ACCESS II RCT research team member to review the consent form with the participant. A trained member of the ACCESS II RCT research team will discuss the study and review information in the written ICF. Time will be allotted for the subject to ask any questions that they

may have about the study. Participants will be encouraged to ask questions that they have about the research prior to signing the ICF. Signed ICF will be obtained through REDCap displayed on the study funded smartphone. A copy of the signed ICF will be sent by text or email to the study funded smartphone, depending on the preference of the participant.

#### In-Person Paper-Based Consent

Only IRB Approved NYU ACCESS II RCT research team members will obtain (electronic or written) informed consent from ACCESS II RCT study participants. IRB Approved ACCESS II RCT Research team members may obtain in-person informed consent at Community-Based Organizations, with the assurance of the CBO. Participants requesting in-person paper based consent will be given the ICF to read and ask questions. Subjects will be required to read, sign and date each page of an IRB-approved ICF with study personnel and will be given a signed and dated copy. The original signed and dated ICF will be kept as source documentation. All study procedures will be explained in non-technical terms to enhance subject understanding of procedures. Subjects have the right to withdraw consent at any time.

**Participants will be informed that their decision to participate or decline to enroll in the study will not affect any services they receive at their clinical site or any other organization.**

Paper copies of consent forms will be kept in locked file cabinets at NYU Meyers. All research data will be kept on a computer that is password-protected in an encrypted file in the locked offices at NYU Meyers. Only the consent form, tracker (locator) form, and tracker computer will link the participant's name to the identification number. Members of the project team will receive intensive training about confidentiality.

**We Will Not be Enrolling Mature or Emancipated Minor Status for Youth Ages 17 and Younger.** The proposed study's research and the consent procedures are consistent with the guidelines for inclusion and protection of adolescents in epidemiological and clinical research. **For the purposes of informed consent, participants will fall into the category of legal adults (aged 18-29 years), who will sign their own consent forms.**

#### **Planned Procedures to Protect Against Risk**

**Confidentiality of Data.** Each study subject will be identified by a random number and not by name, address, social security number and/or medical record number. Data collected on study participants will not be shared with anyone outside of the research team. All data collected will be either entered into password protected computers and/or stored in locked file cabinets with access limited to study team members. After the study is completed, all links between patients and the study will be destroyed.

**Email Correspondence:** All email correspondence containing de-identified PHI will be conducted utilizing the send safe feature within the medical center email system and other approved site-specific secure networks.

**Data Management.** We are using REDCap and built a secure and password-protected web-based database to manage recruitment, eligibility assessment, scheduling, ACCESS II RCT randomization and data collection. Recruitment and study data will be collected and managed using REDCap electronic data capture tools supported by the Health Sciences Library at NYU

Langone Health. Recruitment and response rates will be tracked in real time using REDCap reporting features. REDCap is a secure, web-based application designed to support data capture for research studies, providing 1) an intuitive interface for validated data entry; 2) audit trails for tracking data manipulation and export procedures; 3) automated export procedures for seamless data downloads to common statistical packages; and 4) procedures for importing data from external sources. REDCap is a robust, secure, HIPAA-compliant infrastructure with a consortium of more than 3,500 research partners worldwide.

All confidential information (demographic, survey and viral load data) will be stored electronically in REDCap with access limited to [name] and IRB approved members of the study team. Numeric coding will be used to protect the identity of participants. Electronic files containing patient data and study materials will be backed up daily to protect against computer failure. Self-reported survey data and medically extracted viral load data will be directly inputted into REDCap. All computerized data will be kept on computers that are double password-protected. All study data collected in REDCap will be exported to EXCEL every three months and will be transferred to the NYU Meyers secure server for back-up, which is double password protected and available only to project staff. REDCap is backed up daily on NYU Langone Medical Center's REDCap Administrator to prevent loss of data. **HIPAA Training**. All research team members **including peer health coaches** will pass the protection of human subjects and research HIPAA exams and sign a protocol specific conflict of interest. Additional steps will be taken to protect the vulnerable population in this study. Team members will be trained on content related to New York State Department of Health (NYSDOH) HIV Confidentiality law, <http://www.health.ny.gov/publications/9192.pdf> and will also be expected to view the video entitled, 'Complex Issues with Research Involving Vulnerable Populations' available from the U.S. Department of Health and Human Services', [http://www.hhs.gov/ohrp/education/training/ded\\_video.html#complex](http://www.hhs.gov/ohrp/education/training/ded_video.html#complex). Issues related to human subjects and confidentiality will also be re-reviewed in the training of peer health coaches . This will allow for questions and related discussion.

## DATA AND SAFETY MONITORING PLAN

This study is no more than minimal risk but a data and safety plan is still important to ensure the well-being of the vulnerable population.

**Safety and Monitoring Committee.** In addition to the regular scheduled meetings with the ACCESS study team, a *Safety and Monitoring Committee* (SMC) will be formed. This SMC will be comprised of PI [name] (leading the study), three independent experts as follows: (senior biostatistician/methods researcher; HIV bio-behavioral clinical trialist; health informatics researcher with specialty in mHealth). [name] will provide oversight of the study and will be the senior researcher responsible for monitoring the trial. This committee will meet annually during the 4-year time period to review data adequacy, data analyses, results, and fidelity to the intervention. In collaboration with the other members of the mentorship team, this committee will create an action plan to address any concerns participants may have during the course of the study. In the event of any adverse events, reporting will follow the guidelines of the NYU IRB.

**Protecting Confidentiality of Data.** All participants will receive an identification number and this number will be used for all materials, and assessments. Only the consent forms will directly link the participant's name to participation in the ACCESS II RCT. Given that ClinCard is a type of banking card, procedures for activation include providing the participant name, address, and date of birth. Participants will be informed of these procedures during the informed consent

process.

Source documentation of eligibility criteria including viral load, and verbal consent will be securely uploaded to REDCap by IRB approved staff at the clinical site (these staff members will have been approved for an NYU Keberos ID).

**Exceptions to Confidentiality.** The NYU - University Committee on Activities Involving Human Subjects (UCAIHS) has identified a number of circumstances in which confidentiality cannot be maintained. We cannot maintain the confidentiality of participants in four specific circumstances.

**For participants who have reached the age of majority, that is, who are ages 18 years and older,** confidentiality will not be maintained: (1) in the event the participant has perpetrated sexual abuse on a minor; (2) in the event the participant has perpetrated physical abuse on a minor; (3) if a participant reports current suicidality and is in imminent danger of suicide; and (4) if a participant reports current homicidality or a serious threat of physical harm to others. There are no other circumstances when confidentiality will be violated.

The following actions will be taken if any of these four circumstances is identified:

**Child sexual or physical abuse.** Child abuse will be reported to the local child protective services agency by [name] who is a mandated reporter and complies with New York State Child abuse laws.

**Suicidality.** If participants are at imminent risk for suicide, law enforcement will be notified by Drs. [name] or [name] who will call 911. [name] (contact PI at NYU and licensed clinical psychologist) and [name] (board certified/licensed pediatric nurse practitioner) will Zoom into the videoconferencing session for crisis management.

**Homicidality or a serious threat of physical harm to others.** When participants are at imminent risk for committing homicidal acts, law enforcement will be notified by Drs. [name] or [name] who will call 911. [name] (contact PI at NYU and licensed clinical psychologist) and [name] (board certified/licensed pediatric nurse practitioner) will Zoom into the videoconferencing session for crisis management.

As part of the informed consent process, participants will also be informed that all information they provide in interviews and intervention sessions is confidential with these exceptions. The NYU IRB recommends the following language be used in the Confidentiality section of the consent form:

*“However, if you are in imminent danger of committing suicide or homicide the appropriate agency or authority will be contacted; and, if you are under 18 and currently being sexually or physically abused, or, if 18 or older, physically or sexually abusing someone else, a report will be made to the local child protective services organization or appropriate authority or organization.”*

**Compliance with IRB Requirements.** [name] will lead weekly hybrid team study meetings (in-person with optional Zoom call in procedures for team members off site) during years 1-4. One meeting per month will be directed to monitoring study safety, auditing selected cases for compliance with IRB requirements, conformance with informed consent requirements,

verification of source documents, and investigator compliance. Members of the study team will also participate in these monthly meetings.

## **Regulatory Issues**

### **Reporting to NYU IRB**

Adverse events, serious adverse events, participant complaints that cannot be handled by [name], and any research related injuries will be reported to the NYU IRB consistent with the NYU IRB guidelines. [name] (contact PI at NYU), [name] (lead PI at Stony Brook University) and co-investigators will determine which of the following best describes the event:

- **The event is serious, unexpected (in terms of its nature, frequency or severity) and related or possibly related to participation in the research.**
- **The event is not serious, but is unexpected (in terms of its nature, frequency or severity), related or possibly related to the research and suggests that the research places subjects or others at a greater risk of physical or psychological harm than was previously known or recognized.**

[name] will report an adverse event or serious adverse event as described above (including death of a participant) within 24 hours of discovery of the event by the research team. In the event of a death, the NYU IRB [contact] will be called immediately by telephone. All other events will be reported by email, telephone or fax. *NYU Event Requiring Prompt Reporting to the IRB* forms will be completed and submitted within 72 hours.

### **Reporting of Adverse Events and Serious Adverse Events to NINR**

Adverse events will be reported to the NINR at least once per year as part of the annual progress report. This report will include a description and date of the event and the outcome/resolution. If there are no adverse events, a statement that no adverse events occurred will be included in the progress report.

Serious adverse events will be communicated to NINR within 72 hours and will include: date of the event, what occurred, actions taken by project staff, planned follow up, the time point in study (i.e. focus group or intervention) of the affected participant, whether the event appears to be related to the intervention, and whether the event affects future participation of the study participant.

## **Data Monitoring**

### ***Plans for Interim Analysis of Data***

**Procedures to Ensure the Validity and Integrity of the Data.** All data files received during data collection will be verified weekly by a trained project manager. Data files will be reviewed monthly for quality by Drs. [name] (PI) and [name] (biostatistician) with the assistance of trained project manager. We will examine individual survey data to determine whether some individuals may be having difficulty understanding items on the measures (i.e., refusing to answer more than 5% of survey). We will also review participant responses for possible systemic biases that may result when individuals are not truly responding to items but providing false or random answers. We propose to use STATA to identify possible non-random patterns of missing data. When items, data sources, or staff are associated with more than 5% missing data that are not due to planned interview skip patterns, we will determine the causes of

missing data and implement strategies to reduce it (e.g., retraining of staff). The time to complete different interviews will be summarized to identify participants who took much less or much more time than most others, which may indicate careless responding or difficulty understanding interview items. Also, on a weekly basis, the project manager will review due dates of scheduled intervention sessions and/or data collection visits for enrolled participants, and will inform [name] and peer health coaches about past due interviews.

**Data Safeguards.** Access to NYU Meyers offices ([name] and [name]) is restricted to research staff. The building is secure and monitored by security staff. File drawers containing participant information are kept locked when not in use. Only [name], and the project manager will have keys to these file cabinets. Paper copies of consent forms will be kept in a locked office in a locked cabinet at NYU Meyers.

Consent and other confidential paper forms will be scanned for electronic storage on project-specific folders on the NYU Meyers secure server. The folder is double password-protected and access to project-specific folders is restricted to members of the research team.

All computerized data, including REDCap, (survey measures, viral load, etc.) will be collected using computers that are double password-protected and are only labeled with participant identification numbers. All study data collected in REDCap will be exported to EXCEL on a every three months and transferred to the NYU Meyers secure server for back-up, which is also double password protected and available only to the research team. Peer health coaches will not be entering, cleaning, and/or analyzing data with the primary role of delivering the intervention. Peer health coaches will therefore not require and/or have access to the NYU Meyers shared drive or the REDCap platform. Peer health coaches will be meeting remotely with study participants via HIPAA compliant Zoom videoconferencing as part of the intervention and regularly attend study team meetings.

A master database that contains participant identifying information and participant identification (PID) numbers will be stored on REDCap. This data will be downloaded monthly into a project-specific folder on the NYU Meyers secure server. This folder is double password protected and can only be accessed by the study's staff members. NYU Meyers staff members who are not members of the research team for this study do not have access to this folder.

**Adverse Events.** Federal regulation (21 CFR Part 312) defines an "adverse event" (AE) as any untoward occurrence involving a study participant, or individual connected to the participant, occurring during the course of the study (including the study's follow-up period). Adverse events are categorized as either a Serious Adverse Event (SAE) or an Adverse Event (AE). **Adverse events are defined as negative experiences that do not involve imminent danger. Serious adverse events are negative experiences that involve imminent danger.**

**Adverse events or serious adverse events are not expected during the course of this study.** However, during the ACCESS-II study sessions 4 through 6, peer health coaches will explore participant's history and experiences with HIV stigma and disclosure concerns and related psychological distress and substance use. There is a potential for a participant to experience discomfort, depressive symptoms, anxiety and/or anger during this session and/or any of the ACCESS II RCT sessions. Peers health coaches will receive adequate training and supervision to minimize this potential.

[name] is a highly trained, board certified pediatric nurse practitioner with 15 years of clinical experience in working with HIV+ AYA. [name] (contact PI) is an experienced,

clinically-trained psychologist and will provide expertise in the development of the peer training protocol, allowing for peer health coaches to recognize and report any potential adverse events immediately (such as discomfort, depressive symptoms, anxiety and/or anger). The training protocol will also include content to facilitate recognition of serious adverse events including suicidal/homicidal ideation. As part of this training protocol, peer health coaches will be trained to not act as mental health counselors. Instead they will be instructed to notify [name] immediately who will implement procedures for management of adverse events as described in reporting of adverse events below. In the event of an adverse event, the peer health coach will be delivering the intervention on site from an NYU Meyers designated computer. Additionally, [name] (lead PI), [name] (contact PI), [name] (co-investigator), and [name] (physician collaborator) will be available via cell phone 24 hours per day.

Other potential adverse events may also include participant discomfort with study procedures or inadvertent disclosure by peer health coaches of confidential research information to other persons and/or to staff at NYU Meyers. The potential for discomfort with study procedures will be minimized by training the members of the study team and peer health coaches to be sensitive to the needs of the participants (i.e. taking a 5-minute break, if needed). The potential for inadvertent disclosure by peer health coaches will be minimized by successful completion of the protection of human subjects and research HIPAA exams and by signing a protocol specific conflict of interest.

**Reporting Adverse Events. This study is no more than minimal risk and adverse events are not expected.** In the event of an adverse event during the intervention - remote videoconferencing sessions (i.e. discomfort, depressive symptoms, anxiety and/or anger), the peer health coach will verbally (phone or in person) notify the project manager, [name] and [name] immediately. If the participant is from Jacobi Medical Center, [name] (clinician co-investigator at Jacobi) will be notified immediately to discuss whether or not mental health referral is needed. If the participant is recruited from North Central Bronx, [name] may collaborate with [name] (physician collaborator) to discuss whether or not mental health referral is needed. If the participant is from BronxCare Health System, [name] (physician collaborator at BronxCare Health System) will be contacted, if deemed necessary. If a participant is recruited from other methods of recruitment, the physician of that participant will be contacted, if deemed necessary. For participants recruited from other recruitment sites, [name] with co-investigators will discuss if mental health referral is needed. All participants will be recruited from clinical sites staffed with psychosocial professionals (psychologists, social workers, and one psychiatrist) who would be available if referral to mental health services is needed.

In the event of a serious adverse event such as suicidal or homicidal ideation, the institutional emergency protocol of the clinical sites (Jacobi Medical Center (North Central Bronx Network, and BronxCare Health System), will be followed. This includes immediate referral to 24-hour psychiatric emergency services via the psychiatric emergency room. This protocol also includes referral to a 24-hour crisis number, [name] with counselors available at all times. Additionally, the clinical site would be contacted immediately to notify clinical staff and if the SAE occurs after hours, an on-call physician may be reached 24 hours a day. In the event of an imminent life threatening emergency, 911 would be notified.

As noted in our consent form, we are obligated to break confidentiality of participants in the event of sexual and physical abuse, or if they report current suicidality or homicidality. If participants are at imminent risk for suicide during in-person interview (focus group or post intervention interview), they will be escorted to a hospital emergency room where appropriate,

or law enforcement will be notified. When participants are homicidal, law enforcement will be notified. All such decisions will be made by Drs. [name] and [name] in collaboration with co-investigators.

In the event that such adverse events are reported to [name], he will immediately communicate the event to the Vice Dean for Research at NYU Meyers, and this verbal report will be followed by a written report within 24 hours. The Vice Dean will immediately inform the Chairperson of the NYU Meyers IRB and jointly decide whether the reported event is a Serious Adverse Event (SAE). If the event is deemed to be a SAE, it will be reported to the NINR Project Officer within 72 hours of the event. The written report to NINR will be sent via email or fax. [name] will also follow adverse event reporting procedures for the NYU IRB.

[name] will determine if there is sufficient evidence of an adverse event to necessitate suspension of data collection, further IRB review, and/or modification of the protocol or other changes. If there is sufficient evidence, [name] will immediately discuss the recommendation with the Chairperson of the IRB and reach a determination whether to suspend data collection or to stop the study from proceeding. Resumption shall be based on the concurrence of Drs. [name], [name], co-investigators, the Chairperson of the IRB and the Vice Dean. The Federal Agency (NINR) will receive a written report within 72 hours of any such suspension and/or resumption of data collection.

[name] will provide an annual summary report of all adverse events to the IRB as part of the annual review. NYU Meyers will report all adverse events to the Federal Agency (NINR) as part of the Annual Progress Report. If no adverse events have occurred, the report will state, "*No adverse events affecting human subjects have occurred during this project year.*" As described above, SAEs will be reported to NINR within 72 hours of the event. [name] is ultimately responsible for the Data and Safety Monitoring Plan as well as the NYU IRB.

**Expertise of the Investigative Team.** The lead PI ([name]), contact PI ([name]), co-investigator ([name]), and physician collaborator ([name]) have conducted many intervention studies, including those with populations of youth at risk. They are highly experienced in managing research issues with vulnerable youth during the course of an intervention, and with assessing sensitive topics while maintaining confidentiality and ethical standards. As a result, the ACCESS II RCT study team is well equipped to exercise excellent decision making and thoughtful consideration on all study related matters.

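### Imminent danger is the only stated test for a serious adverse event, so an admission or lasting harm can be labelled non-serious and be guaranteed to reach the funder only in the annual report

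*Combined protocol and SAP*

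**What the plan says.** The Adverse Events paragraph (under Data Monitoring, Plans for Interim Analysis of Data) opens broadly: any untoward occurrence during the study or its follow-up counts as an adverse event. It then divides events in two: "Adverse events are defined as negative experiences that do not involve imminent danger", whereas "Serious adverse events are negative experiences that involve imminent danger".

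The section on reporting to NINR ties speed to that label. For ordinary events, "Adverse events will be reported to the NINR at least once per year as part of the annual progress report". For the others, "Serious adverse events will be communicated to NINR within 72 hours". The later Reporting Adverse Events text repeats both routes: "NYU Meyers will report all adverse events to the Federal Agency (NINR) as part of the Annual Progress Report", and for an event deemed serious, "it will be reported to the NINR Project Officer within 72 hours of the event". Under that text the Vice Dean for Research and the IRB Chairperson decide together whether a reported event is serious.

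Reporting to the NYU IRB is a separate route. Its first category reads "The event is serious, unexpected (in terms of its nature, frequency or severity) and related or possibly related to participation in the research". Its second covers non-serious events that are unexpected, related or possibly related, and suggestive of greater risk than was known. Events so described, and deaths, go to the IRB within 24 hours of discovery.

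**The concern.** Imminent danger describes how threatening a situation is, not how grave the result was. A trial can have a participant admitted to hospital, or left with lasting impairment, without imminent danger having been part of the event. The plan's literal wording puts such an event in the same class as passing discomfort in a session.

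Two things are at stake. The first is how soon the funder learns of a grave event in a group the plan itself calls vulnerable, in a trial whose sessions 4 to 6 are acknowledged to carry a potential for distress. The second is the meaning of the serious-event count: if staff apply different readings of the word, the count does not measure the same thing across participants or arms.

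**Working it through.** The question is one of classification, so the check sets the relevant sections side by side.

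**Step 1: is there a second definition?** The places that use the term are the Safety and Monitoring Committee paragraph, Reporting to NYU IRB, Reporting to NINR, the Adverse Events paragraphs (including coach training) and Reporting Adverse Events. None makes inpatient admission, lasting disability or a comparable outcome a criterion. Death is named only in the IRB rule.

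**Step 2: follow typical events through the rules.**
- *Danger present when the study learns of it:* serious; NINR within 72 hours.
- *Admission with no imminent danger at any time:* non-serious on the literal wording; annual report guaranteed.
- *Lasting disability without imminent danger:* the same.
- *Life-threatening admission, over when disclosed at week 12 or 24:* undetermined. The wording does not say whether danger at the time of the event is enough. If it is, the event is serious; if not, it falls to the annual report.
- *Suicidal or homicidal ideation without imminence:* non-serious under the definition, but serious under the coach-training text and Reporting Adverse Events, which give ideation as an example with no imminence condition.

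**Step 3: do the other routes close the gap to NINR?**
- The joint decision could class an admission as serious, but the only criterion available to it in these documents is the one above.
- The 24-hour route goes to the IRB. Apart from deaths, both its categories require the event to be unexpected and at least possibly related, and the first also depends on the undeveloped word serious.
- NINR also receives a report within 72 hours of any suspension of data collection, but only if a suspension is ordered.
- The Safety and Monitoring Committee meets annually.

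**Step 4: compare the clocks.** The IRB rule runs from discovery. The NINR section gives 72 hours with no start point. Reporting Adverse Events runs the 72 hours from the event. A serious event learned of on day 4 or later is therefore already late under the last rule. This can readily arise: survey assessments are at baseline, 12 and 24 weeks, the sessions span eight weeks, and the control arm uses an asynchronous platform.

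**Scale, for illustration only.** Full follow-up of everyone gives 120 × 24/52.18 = 55.2 person-years. At an assumed 5 to 15 admissions per 100 person-years, this is 55.2 × 0.05 = 2.8 to 55.2 × 0.15 = 8.3 admissions. The rate is not from the documents, dropout would lower the figures, and how many would lack imminent danger is unknown. The point does not rest on this range.

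**The case against.** The strongest reply is that the plan is less rigid than its definition looks. A reader might infer that any event already over when disclosed is automatically non-serious. The documents do not say so: an event that was dangerous when it happened can still be said to involve imminent danger, and the same paragraph covers follow-up. Nor is classification automatic, given the joint decision. The treatment of ideation shows that the study team uses the term more widely than it defines it. All of this stands, and it limits the point to what the wording permits, not what it compels.

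Other stronger readings also fail. Ordinary events do not go to NINR only once a year: annual is a stated minimum. Grave events are not kept from everyone, since unexpected and possibly related ones can reach the IRB within 24 hours of discovery. Nor could a known admission be hidden behind a clean report: the prepared statement says that no adverse events of any kind occurred, and the annual report must describe each event and its outcome. The effect is delay and mislabelling, not concealment.

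It is also fair that the NYU IRB guidelines, to which the plan refers, may define seriousness. They are not part of these documents, so that cannot be judged, and neither can agreement with the federal regulation cited. Finally, the study is described as minimal risk and no efficacy result is affected.

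None of this supplies an outcome criterion, or a guaranteed prompt route to NINR for an event labelled non-serious.

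**Conclusion.** The point holds in a limited form. The documents contain one criterion for seriousness and no outcome-based one. An admission or lasting harm that involved no imminent danger can be classed as non-serious. Where the danger had passed, the text is ambiguous and the same label is possible. The guaranteed time to NINR then lengthens from 72 hours to the next annual progress report. The number of events affected cannot be derived from the documents.

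Separately, the sections disagree on whether ideation needs imminence to be serious and on when reporting time starts. Those inconsistencies need reconciling whatever the event rate. The conclusion assumes that no other definition of seriousness governs the trial; one in the unseen IRB guidelines would reduce the practical effect but would still need to be cited. The change is worth making because it is cheap, although it does not bear on the primary analysis.

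**What to change.** Replace the two bold definitional sentences in the Adverse Events paragraph with one outcome-based definition of seriousness for reporting: death, a life-threatening event, inpatient admission, lasting disability, or an event judged comparably important. State that it applies whenever the study learns of the event, whether or not danger is still present.

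Use that definition in Reporting to NYU IRB, Reporting to NINR, the coach-training text and Reporting Adverse Events, and name it as the standard for the joint decision. State how suicidal or homicidal ideation is classified for reporting, so that the definition and the examples agree. Run the 72-hour NINR clock from discovery in both places where it appears.

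The cost is about a paragraph of wording, matching edits and a few more expedited reports. Emergency procedures, clinical management, sample size and analysis are untouched. The definition will not by itself bring undisclosed admissions to light, because the measures listed for weeks 12 and 24 do not ask about them.
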